7.2 PARTICIPANT DISCONTINUATION/WITHDRAWAL FROM THE STUDY

Study Treatment Discontinuation

Under certain circumstances, an individual participant’s receipt of study product will be prematurely or permanently discontinued. Specific events that will result in stopping a participant’s infusions or VOR dosing in this study include:

- Failure to meet requirements established for safety assessment
- Withdrawal from the study
- Pregnancy
- Grade 3 AE assessed as related to the study products (with the exception that self-limited Grade 3 solicited reactogenicity does not require discontinuation from VRC07-523LS administration).
- Grade 4 AE assessed as related to the study products
- Intercurrent illness that is not expected to resolve prior to the next scheduled VRC07-523LS administration which is assessed by the study PI (or designee) to require withdrawal from the administration of VRC07-523LS
- Repeated failure to comply with protocol requirements
- Co-enrollment into a study in which other investigational research agents will be administered before the participants has completed the follow-up visits after receiving the last study product
- Investigator discretion
- Clinically significant hypersensitivity or infusion-related reaction including but not limited to type 1 hypersensitivity reaction, urticaria, or serum sickness associated with study treatment.

If the study Principal Investigator (or designee) decides that a participant should be withdrawn from study treatment, the protocol team must be alerted within 24 hours. All participants who discontinue treatments should comply with protocol-specified visits and follow-up as required by the protocol and evaluation by the study PI (or designee). The only exception to this requirement is when a participant withdraws consent for all study procedures or loses the ability to consent freely (i.e., is imprisoned or involuntarily incarcerated for the treatment of either a psychiatric or physical illness).

If a participant is withdrawn before completing the study, the reason for withdrawal must be documented appropriately in the study documents.

Early Study Discontinuation

A participant may withdraw or be withdrawn from the study if any of the following occurs:

- Failure by the participant to attend multiple clinic visits.
- Failure to receive the first VRC07-523LS infusion.
- Development of an illness that requires treatment with medications prohibited in this study.

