Study specific safety and research assays will be collected at the research visits. Safety and clinically relevant labs will be performed at UNC McLendon Laboratories or LabCorp. Research assays will be processed and stored in associated research laboratories. Additional details on collection, processing, storage, and shipping of laboratory samples will be provided in the Study Specific Laboratory Manual.

End of Treatment/End of Study Visit

An End of Study (EOS) visit should occur approximately 2 - 4 weeks after Visit 12 depending on ability to follow the participant and duration and severity of ongoing AEs. An individual participant will be considered to have completed the study if the participant was followed through their last protocol-specified visit/assessment (EOS). Participants who have treatment discontinued due to a DLT or other clinical event will be followed on study until the clinical event is resolved or deemed stable and irreversible. Participants will complete the EOS visit per the SOE (section 1.3) but will be followed as necessary for acceptable resolution of the clinical event.

Participants will be considered not to have completed the study if consent was withdrawn, the study Principal Investigator discontinues the participant from study for severe lack of compliance, or the participant was lost to follow-up.

A list of evaluations to be performed for the EOS visit is provided in the SOE in section 1.3. The EOS Visit should be performed after the participant has met off-study criteria, or has been followed for at least 7 weeks after the last VRC07-523LS dose. Participants experiencing an unresolved AE will be followed until the AE is either resolved or deemed stable and irreversible.

Research Laboratory Assays

The ability of VRC07-523LS infusion in combination with multiple doses of VOR to alter markers of persistent HIV-1 infection in individuals on suppressive ART will be evaluated by measurement of: a) the frequency of resting CD4 T cell infection by QVOA and b) levels of plasma HIV-1 RNA, as measured by low levels of an HIV-1 RNA assay.

Resting CD4 T Cell Infection (RCI)

Lymphocytes are obtained by continuous-flow leukapheresis (samples obtained as per the SOE, section 1.3) and resting CD4 T cells are isolated as previously described (57).

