Hemoglobin, hematocrit, white blood cell count (WBC), differential WBC, absolute neutrophil count (ANC), and platelet count will be performed in real time at the local laboratory.

STAT CBC with differential is required prior to each leukapheresis procedure done at UNC unless completed within 24 hours of the procedure and the results of that test are available to the Apheresis Lab. Apheresis collections completed at the American Red Cross require a CBC within the 30 days prior to the procedure.

Liver Function Tests

Total bilirubin, AST (SGOT), ALT (SGPT), and alkaline phosphatase will be performed in real time at the local laboratory.

NOTE: For participants on ritonavir boosted atazanavir, total and direct bilirubin should be measured.

Blood Chemistries

Screening lab evaluation are done fasting and includes electrolytes (sodium, chloride, potassium, CO₂/bicarbonate), glucose, blood urea nitrogen (BUN), creatinine, calcium, albumin, magnesium, lipase, and total protein in real time at the local laboratory.

Safety lab evaluations throughout the study include electrolytes (sodium, potassium, chloride, CO₂/bicarbonate), BUN, creatinine, calcium, magnesium, and glucose (also reference Pre-Infusion Safety Lab Assessment).

Creatinine and Creatinine Clearance

Creatinine clearance (eGFR) calculations will use the CKD-EPI equation. This calculation can be found at https://www.qxmd.com/calculate/calculator_251/egfr-using-ckd-epi

The creatinine clearance (eGFR) will be required for study enrollment eligibility. The study assesses serum creatinine level at all of the safety lab checks and uses the serum creatinine value for toxicity grading.

The creatinine clearance (eGFR) value reported as part of the lab report of serum creatinine level will be re-assessed and re-calculated if incidental finding indicates a value \geq Grade 3. The re-calculated value using the CKD-EPI equation will be used to determine the severity of the lab abnormality.

Pre-Study Treatment Safety Lab Assessments

Participants will have a Pre-Study Treatment Safety Lab Assessment prior to receipt of VRC07-523LS infusions at Day 0 and Day 60. The safety lab results obtained in this assessment must be within the eligibility criteria parameters established for this study. Labs that fall outside the parameters can be repeated one time only to qualify the participant to proceed on study.

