After repeat testing, any lab value that remains outside the guidelines but considered clinically non-significant and documented as such by the study clinical PI (or designee), must be reviewed and approved by the protocol team and/or safety committee prior to the infusion.

Time points for the Pre-Study Treatment Safety Lab Assessment are:

- Step 2, Day 0 – prior to the administration of the first infusion. These labs can be performed up to 7 days prior to the infusion.
- Step 3, Visit 7, Pre-Visit – prior to the administration of the 2nd VRC07-523LS infusion

Follicle Stimulating Hormone (FSH) Test

This test is done at screening to document menopause in women who have been without a period for > 12 months.

Serum Pregnancy Test

A negative serum pregnancy test (to rule out pregnancy) is required on all women at screening.

A negative serum pregnancy test is required at each visit prior to VRC07-523LS infusion, and within 72 hours of the first VOR dose in Step 2 and Step 3 regardless of documented procedures that prohibit pregnancy.

In addition, a serum pregnancy test should be performed at any time if pregnancy is suspected. Because the study has no direct clinical benefit, this added protection is warranted.

Hepatitis Screen

Both hepatitis tests (HCV AB and HBsAg) must be negative or non-detected to be included on the study. A positive HCV AB test reflexed to Hepatitis C RNA revealing a negative result is acceptable.

Eligibility will be determined based on negative testing, per above definition at screening and prior to the Day 60 visit.

RPR

This test is done to rule out clinically active untreated syphilis at screening.

Participant may participate on study following documentation of adequate treatment of syphilis at screening (Visit 1). Participants diagnosed with syphilis while on study, will be referred for and require documentation of treatment prior to the 2nd infusion at Day 60. These infusions can be delayed until a minimum of 14 days post treatment for syphilis per recommendation by the study PI (or designee).

Fasting Lipid Panel

Total cholesterol, HDL, LDL calculation, VLDL calculations and triglycerides are obtained at screening.

Prothrombin Time (PT), INR, and APTT

Evaluated at the Screening Visit.

CD4⁺/CD8⁺

All study required absolute CD4⁺/CD8⁺ count and percentages must be obtained from a laboratory that possesses a CLIA certification or equivalent.

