- Laboratory values that fall outside of a clinically accepted reference range or differ significantly from previous values must be evaluated for clinical significance by the Investigator (or designee). The Investigator (or designee) may repeat the laboratory test or request additional tests to verify the results of the original laboratory tests.
- If the Investigator (or designee) determines the laboratory value is an abnormal change from baseline and is of clinical significance for that participant, it is considered an AE.
- Generally, Grade 1 and Grade 2 laboratory findings need not be reported as AEs unless deemed clinically significant by the Investigator (or designee).
- Consistent with the DAIDS designation of Grade 3 events as severe or medically significant and Grade 4 events as life-threatening, Grade 3 and Grade 4 laboratory findings should be reported as AEs or SAEs, as appropriate.

- The test result or finding should be reported as the AE. Such laboratory values should generally be recorded as “increased” or “decreased” (e.g., change from baseline potassium of 5.0 to 3.5 mEq/L = potassium decreased).

The study PI (or designee) is responsible for appropriate reporting of adverse events to the regulatory authorities. The study PI (or designee) will also report all suspected unexpected serious adverse reactions. The study PI (or designee) must report suspected unexpected serious adverse reactions to the UNC IRB, unless otherwise required and documented by the UNC IRB.

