8.3.5 ADVERSE EVENT REPORTING

Adverse events will be graded according to the DAIDS Table for Grading the Severity of Adult and Pediatric Adverse Events (DAIDS AE Grading Table), corrected Version 2.1, July 2017, on the DAIDS RSC website at <http://rsc.tech-res.com/clinical-research-sites/safety-reporting/daids-grading-tables>

Participants will be monitored for adverse events. Toxicities will be characterized in terms including duration, intensity, and time to onset. Safety endpoints will include all adverse experiences, in addition to laboratory safety assessments, and vital signs. All AEs will be recorded on the appropriate study form. All AEs will be recorded in the database if any of the following criteria have been met:

- Study-related grade ≥ 1 AEs
- Grade ≥ 3 AEs
- Autoimmune-related AEs regardless of grade
- HIV viral loads ≥ 50 copies/mL
- Infusion reactions regardless of grade
- AEs that led to a change in study intervention regardless of grade
- AEs meeting SAE definition or EAE (Expedited Adverse Event) reporting requirement

Grade 1 or 2 Toxicity

Participants who develop a Grade 1 or 2 AE or lab toxicity that occurs following a VRC07 infusion or dose of VOR dosing that is thought to be possibly, probably, or definitely related to study treatment should be discussed with the study team. Grade 1 or 2 AEs that may be related to the VRC07-523LS or VOR should be handled according to standard clinical practice and documented. Participants who experience a Grade 1 or 2 AE that is judged related to the study treatments by the study PI (or designee), may continue study treatment at the discretion of the study PI (or designee).

Participants who experience a Grade 1 or 2 AE that is judged not to be related to the study drug/product by the study PI (or designee), may continue study treatment at the discretion of the study PI (or designee).

Grade 3 Toxicity

For participants who develop a Grade 3 AE following administration of VRC07-523LS or VOR that is judged by the study PI (or designee) to be at least possibly study treatment-related, the protocol team, inclusive of the DAIDS Medical Officer, must be notified within 24 hours. Participants experiencing Grade 3 AEs should be followed closely and if the AE does not return to Grade ≤ 2 within 2 weeks, the study team should again be notified within 24 hours and the SMC will be notified. Continued receipt of study

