The protocol team, inclusive of the DAIDS Medical Officer, should be contacted within 24 hours of notification of any reactions thought definitely, possibly, or probably related to the VRC07-523LS infusion.

Infusion Site reaction

Infusion Site Erythema or Redness and Infusion Site Induration or Swelling will not be considered interference with usual social and functional activities such that:

- Grade 1 is: 2.5 to < 5 cm in diameter OR 6.25 to < 25 cm² surface area;
- Grade 2 is: ≥ 5 to < 10 cm in diameter OR ≥ 25 to < 100 cm² surface area;
- Grade 3 is: ≥ 10 cm in diameter OR ≥ 100 cm² surface area OR Ulceration OR Secondary infection OR Phlebitis OR Sterile abscess OR Drainage;
- Grade 4 is: Potentially life-threatening consequences (e.g., abscess, exfoliative dermatitis, necrosis involving dermis or deeper tissue)

Allergic or Hypersensitivity Reactions

Record all allergic and hypersensitivity reactions with both grade severity and attribution.

Serious allergic or hypersensitivity reactions (≥ Grade 3) that are deemed possibly related to the study treatment by the study PI (or designee) will be reported to the protocol team and SMC within 24 hours of notification and to the NIH, UNC IRB, FDA, and study product sponsors within 48 hours per their reporting requirements.

Dose Limiting Toxicity (DLT)

- Hematologic dose-limiting toxicity will be defined as any confirmed toxicity ≥ Grade 2, that cannot clearly be attributed to another reversible cause. These participants will not receive further doses of VOR or VRC07-523LS.
- Follow participants per protocol schedule of events until the lab abnormality or toxicity resolves to ≤ Grade 1 or the participant's baseline.
- Non-hematologic dose-limiting toxicity will be defined as any confirmed symptomatic ≥ Grade 3, if related (definitely, probably, or possibly) to VOR or VRC07-523LS

Monitoring HIV RNA levels

In the event of viremia of ≥ 50 copies/mL the following should occur per standard of care:

- Adherence to ART should be carefully assessed and documented.
- A standard HIV RNA assay should be repeated within 1-4 weeks.
- HIV resistance testing will be performed at the time of drawing a confirmatory sample.
- HIV RNA will be repeated every 2 weeks, or sooner as clinically indicated, until <50 copies/mL and the participant can continue on study.

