- If persistent viremia is documented, ongoing administration of study treatment will be reviewed on a case-by-case basis with the participant, their HIV provider, and the study team.

In the event of confirmed viremia and documented adherence to ART, ART should be managed by the primary care provider in discussion with the study team. The results of the HIV resistance tests will be shared with the participants and their care providers.

Immediately Reportable Events

Immediately Reportable Events (IREs) are events that must be reported immediately to the sponsor within 24 hours of the study site's awareness of the event:

- All SAEs
- Pregnancy in a study participant or partner of a study participant

- All \geq Grade 2 Cytokine Release Syndrome/Infusion-Related Reactions
- Administration of a dose significantly greater (specifically, + 20 % or higher) than the planned dose, and results in an event of clinical consequence
- AEs leading to permanent discontinuation of study drug in an individual participant
- Withdrawal of the participant from study drug administration during or after receipt of any doses of VRC07-523LS or VRC07-523LS in combination with VOR for any reason
- Product quality issues with an associated clinical consequence.

In those cases, in which the IRE is considered related to study drug, the study drug may be discontinued and the participant will continue participation in the study for observational safety and analysis (except for cases where the participant is withdrawn from the study by the study PI (or designee) or withdrew their consent). At any time after completion of the study, if an Investigator becomes aware of a serious adverse event that s/he suspects is related to study drug, the study PI (or designee) should report the event to NIH, VRC, Merck, FDA, and the UNC IRB, if applicable.

The study PI (or designee) is responsible for appropriate reporting of AEs to the regulatory authorities.

The Protocol Core Team will monitor the conduct and safety of the study via monthly meetings and regular summaries. Accrual, baseline characteristics, conduct of the study (including premature study discontinuations), any interruptions of ART, virologic failures, and all reported toxicities and events will be monitored during the study and discussed with the protocol team on a monthly basis or more frequently, if needed.

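### Section 8.3.5 gives two dosing instructions for a confirmed Grade 2 hematologic toxicity: continue at PI discretion, or stop both products

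*Combined protocol and SAP*

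**What the plan says.** Two parts of section 8.3.5 of the combined protocol and SAP apply.

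- **Grade 1 or 2 Toxicity.** The paragraph opens with adverse events and laboratory toxicities of these grades after either product. Those thought related are to be discussed with the study team. A participant with a Grade 1 or 2 event, whether judged related or unrelated, "may continue study treatment at the discretion of the study PI (or designee"). Hematologic events are not excepted and the DLT definition is not mentioned.
- **Dose Limiting Toxicity.** A hematologic DLT is a confirmed toxicity of Grade 2 or above that cannot clearly be put down to another reversible cause. The instruction is "These participants will not receive further doses of VOR or VRC07-523LS".

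Related text elsewhere:

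- Section 2.3.1 says that if hemoglobin or platelets fall on vorinostat (VOR), the event is evaluated and dosing is maintained or ended. It gives no grade.
- Section 7.2 introduces its stopping events with "infusions or VOR dosing in this study include". It lists related Grade 3 and Grade 4 events but no hematologic DLT.
- Section 8.1 (end of study visit) says: "Participants who have treatment discontinued due to a DLT or other clinical event will be followed on study".
- Section 8.2 sets a laboratory check before each infusion: "The safety lab results obtained in this assessment must be within the eligibility criteria parameters established for this study". One repeat is allowed. A value still outside the limits but judged clinically non-significant "must be reviewed and approved by the protocol team and/or safety committee prior to the infusion".

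**The concern.** For one foreseeable event the two rules point in different directions. Section 2.3.1 names cytopenias as one of three major categories of adverse experience attributed to VOR and describes anemia and thrombocytopenia as dose-related. An investigator with a confirmed Grade 2 cytopenia would naturally look under the heading for that grade. There the text offers discretion and does not mention that the same event is defined as dose-limiting later in the section.

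At stake are further home VOR doses after an event the protocol itself treats as a reason to stop, and how fast the sponsor hears of it. The trial's primary objective is safety and section 2.3.2 states no direct benefit to participants, so a mandatory stop should not be open to a contrary reading.

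**Working it through.** **1. Where the rules collide.** No sample size, rate or power figure is involved, so the first check is a comparison of cases.

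| Event | Grade 1 or 2 paragraph | DLT text | Conflict |
|---|---|---|---|
| Grade 1, any kind | may continue | not a DLT | no |
| Grade 2, non-hematologic | may continue | not a DLT (threshold is Grade 3) | no |
| Grade 2 hematologic, unconfirmed or clearly due to another reversible cause | may continue | not a DLT | no |
| Grade 2 hematologic, confirmed, no clear other reversible cause | may continue | stop both products | **yes** |

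The finding must also count as an adverse event. Section 8.3.4 says "Grade 1 and Grade 2 laboratory findings need not be reported as AEs unless deemed clinically significant". Grade 3 is outside this point because section 7.2 already stops related Grade 3 events.

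**2. Is precedence stated?** Section 2.3.1 gives no grade, so it does not settle the matter. Section 7.2 is silent on the hematologic DLT. Section 8.1 treats a DLT as a cause of discontinuation, which fits the DLT rule governing but does not say so. The letters of amendment, as supplied, change neither rule.

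**3. VOR doses exposed.** Inputs: first dose on Day 2 or Day 62, every 72 hours, 10 doses per series (section 1.1); blood counts on Days 7, 14, 29, 67, 74 and 89 and at the Pre-Visit (section 1.3); dispensing under Letter of Amendment 2. Days are nominal, and a dose due on the day of a count is treated as taken.

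- Dose *k* falls on Day 2 + 3(*k* − 1) in series 1: Days 2, 5, 8, 11, 14, 17, 20, 23, 26, 29. In series 2 it falls on Day 62 + 3(*k* − 1): Days 62, 65, 68, 71, 74, 77, 80, 83, 86, 89.
- After a Day 7 count, the doses up to the next scheduled count are Days 8, 11 and 14 = **3**. After Day 67 they are Days 68, 71 and 74 = **3**.
- After a Day 14 count, the doses left are Days 17, 20, 23, 26 and 29 = **5**. After Day 74 they are Days 77, 80, 83, 86 and 89 = **5**.
- After Day 29, Day 89 or the Pre-Visit, **0** doses are left in the series.

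Cross-check with dispensing: series 1 is 2 (Day 0) + 3 (Day 7) + 5 (Day 14) = 10. Series 2 is 5 (Day 60) + 5 (Day 74) = 10; by Day 67 two are taken, leaving 5 − 2 = 3 in hand. Both agree. These are maxima, because the DLT definition requires confirmation, which takes time.

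**4. Second infusion.** It cannot be given on the grade paragraph alone, because the section 8.2 check stands in front of it. That check does not govern home doses within a series. A value that has recovered by the Pre-Visit would also pass it, although the DLT rule makes no exception for recovery.

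**5. Reporting.** Stopping brings the event under the Immediately Reportable Events list, which includes "AEs leading to permanent discontinuation of study drug in an individual participant" and requires notice to the sponsor within 24 hours. A related Grade 2 event in a participant who continues is discussed with the study team, entered in the database and reviewed monthly. Section 8.3.5 separately asks for protocol-team contact within 24 hours for reactions thought related to the infusion, whatever the grade. The difference is therefore clearest for events attributed to VOR alone.

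**6. Endpoint.** The primary endpoint and the 1-of-12 criterion count related events of Grade 3 or higher. A Grade 2 event does not enter either.

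**The case against.** The best defense is that this is not a true contradiction. One rule permits continuation and the other forbids it, so a PI who stops complies with both. Reading the DLT text as governing is also the only way to give its Grade 2 threshold any effect. That stands as the probable intent. It does not mend the grade paragraph, which as written gives the wrong dosing instruction for this event.

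Other safeguards exist. Section 8.1 asks that safety laboratory tests be reviewed before study drug is given, and section 7.2 lists inability to take VOR because of a laboratory value as a reason to delay an infusion. These make it likely that the value is seen, but neither says whether dosing stops.

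A reader might infer more than the documents support:

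- *That 8 doses (3 + 5) could follow a Day 7 or Day 67 count unchecked.* A new blood count is due at Day 14 or Day 74, and the last 5 doses are dispensed only then. Reaching 8 needs a second discretionary decision.
- *That most of the remaining regimen, including the second infusion, is exposed.* That needs the value to recover or be approved at the section 8.2 check as well, so it is not a fair measure of size.
- *That section 7.2 contradicts the DLT rule by omission.* Its list is introduced as a non-exhaustive one.

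**Conclusion.** The text is wrong as written, and the point is minor. It covers only a confirmed Grade 2 hematologic adverse event not clearly due to another reversible cause. Per affected participant, the most that could follow from a single decision to continue is about 3 home VOR doses after Day 7 or Day 67, or 5 after Day 14 or Day 74. This assumes nominal visit days and no time lost to confirmation. The reporting difference is real mainly for events attributed to VOR alone.

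The number of participants affected cannot be estimated, because the documents give no Grade 2 hematologic rate for this population. Section 2.3.1 reports only mild VOR-related toxicity in the site's own studies, and section 9.4.1 reports no event above Grade 1 in a prior multi-dose study, so it may be few or none. The primary endpoint, the 1-of-12 criterion and the safety population (anyone receiving at least one dose) are unaffected.

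**What to change.** In the Grade 1 or 2 Toxicity paragraph of section 8.3.5, after the sentences allowing continuation, add: *except hematologic toxicity meeting the DLT definition below, for which VOR and VRC07-523LS are both stopped*. Adding hematologic DLT to the section 7.2 list is optional and for consistency only. The cost is one clause of protocol wording. Design, sample size and analysis do not change.
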